12.2 SANDE derivation

The SANDE questionnaire is comprised of two questions:

- How often do your eyes feel dry and/or irritated?
- How severe you feel your symptoms of dryness and/or irritation are?

This questionnaire uses a 100 mm horizontal line for each question to assess ocular discomfort and/or dryness experienced by the patients. In the SANDE questionnaire, frequency of symptoms ranges from “rarely” to “all of the time” and the severity of symptoms ranges from “very mild” to “very severe”. Patients are asked to place a mark on the two given lines based on the extent of their symptoms.

The locations of the marks made by the patients on the 100 mm horizontal lines will be measured in mm from left to right and recorded as frequency and severity score, respectively.

The global SANDE score will be calculated by multiplying the frequency score by the severity score and obtaining the square root.

12.3 IDEEL derivation

IDEEL is a 57-item questionnaire developed by Abetz et al. [3], that assess the impact of dry eye symptoms on everyday life. The possible range of each IDEEL score was 0 (complete disability) to 100 (no disability). This questionnaire consists of 3 modules:

- Dry eye Treatment satisfaction & Bother (10 questions) comprising two sections: “Treatment – In General” and “Treatment- Eye drops”.
- Dry eye Quality of Life (27 questions) comprising three sections: “Daily activities”, “Feelings” and “Work”.
- Dry eye Symptom Bother (20 questions).

Rules for the calculation of the IDEEL dimension scores are reported in Table 4 and Table 5.

Table 4: Calculation of IDEEL dimension scores

Parameter	Calculation
Item scaling	
 Dry Eye Treatment Satisfaction module: 
 Items 1-5 are scored on a 5-point Likert-like scale from 0 “none of the time” to 4 “all of the time” Items 6, 8-10 are scored on a 5-point Likert-like scale from 0 “all of the time” to 4 “none of the time” Item 7 is scored on a dichotomous scale: 1 “Yes”, 0 “No”. This item is not included in the calculation of the scores. Dry Eye Impact on Daily Life module: 
 Items 1-9 are scored on a 5-point Likert-like scale from 1 “all of the time” to 5 “none of the time”. Patients can also answer “I can no longer do this activity due to my dry eyes” (scored 0) or “I did not do this activity for reasons other than my dry eyes / Not applicable” (coded 6 but scored 5 for calculation of the scores) Items 10-21, 23-27 are scored on a 5-point Likert-like scale from 0 “all of the time” to 4 “none of the time” Item 22 is scored on a dichotomous scale: 1 “Yes”, 0 “No”. This item is not included in the calculation of the scores Dry Eye Symptom-Bother module: 
 Item 1 is scored on a 5-point Likert-like scale from 0 “none of the time” to 4 “all of the time” Items 2-20 are scored on a 4-point Likert-like scale from 1 “not at all” to 4 “very much”. Patients can also answer “I did not have this symptom / Not applicable” (scored 0).
Weighting of items	All items are given equal weight in the calculation of the scores.
Range of scores	0-100 scales.
Scoring procedure	
 Dry Eye Treatment Satisfaction module: 
 Satisfaction with Treatment Effectiveness score: If patients never use treatment for their dry eyes (answer is 0 “none of the time” to item 1) then items 2-5 are missing, and the Satisfaction with Treatment Effectiveness score is missing. The Satisfaction with Treatment Effectiveness score is calculated if at least 50% (2 items) of the 4 items within the dimension are completed, non-missing; otherwise the score is set to missing. The Satisfaction with Treatment Effectiveness score is calculated as the mean of the non-missing item scores 2-5 multiplied by 25. Treatment-Related Bother score: If patients never use treatment for their dry eyes (answer is 0 “none of the time” to item 1) then item 6 is missing. If patients never use eye drops to treat their dry eyes (answer is 0 “No” to item 7) then items 8-10 are missing, and the Treatment-Related Bother score is missing. The Treatment-Related Bother score is calculated if at least 50% (2 items) of the 4 items within the dimension are completed, non-missing; otherwise the score is set to missing. The Treatment-Related Bother score is calculated as the mean of the non-missing item scores 6, 8-10 multiplied by 25. Dry Eye Impact on Daily Life module: 
 Impact on Daily Activities score: Response “I did not do this activity for reasons other than my dry eyes / Not applicable” for items 1-6 is re-coded 5 instead of 6. Other responses are scored with the original response code. The Impact on Daily Activities score is calculated if at least 50% (3 items) of the 6 items within the dimension are completed, non-missing; otherwise the score is set to missing. The Impact on Daily Activities score is calculated as the mean of the non-missing item scores 1-6 multiplied by 20. Emotional Impact score: The Emotional Impact score is calculated if at least 50% (6 items) of the 11 items within the dimension are completed, non-missing; otherwise, the score is set to missing. The Emotional Impact score is calculated as the mean of the non-missing item scores 10-20 multiplied by 25.

Parameter	Calculation
	
 ○ Impact on Work score: If patients are not currently working (answer is 0 "No" to item 22) then items 23-27 are missing, and the Impact on Work score is missing. The Impact on work score is calculated only when patients answer "Yes" to "Are you currently working?". The Impact on Work score is calculated if at least 50% (3 items) of the 5 items within the dimension are completed, non-missing; otherwise the score is set to missing. The Impact on Work score is calculated as the mean of the non-missing item scores 23-27 multiplied by 25. • Dry Eye Symptom-Bother module: 
 ○ The Symptom Bother score is calculated if at least 50% (10 items) of the 20 items within the dimension are completed, non-missing; otherwise the score is set to missing. The Symptom Bother score is calculated as the mean of the non-missing item scores 1-20 multiplied by 25.
Interpretation and method of treating missing data	All the scores are calculated only if at least 50% of the items of the dimension are completed; otherwise, the scores are missing.

Table 5: Summary of dimensions and clusters of items of the IDEEL questionnaire

Module	Dimensions	Number of items	Cluster of items	Direction of dimension scores
Dry Eye Impact on Daily Life	Impact on Daily Activities	6	1-6	Higher score = less impact on daily activities
	Emotional Impact due to Dry Eye	11	10-20	Higher score = less emotional impact
	Impact on Work due to Dry Eye	5	23-27	Higher score = less work impact
Dry Eye Symptom-Bother	Dry Eye Symptom-Bother	20	1-20	Higher score = greater symptom bother
Dry Eye Treatment Satisfaction	Satisfaction with Treatment Effectiveness	4	2-5	Higher score = greater satisfaction with treatment effectiveness
	Treatment- Related Bother / Inconvenience	4	6, 8-10	Higher score = less treatment related bother

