7.2.4 Full Analysis set (FAS)

The FAS population will consist of all randomized patients who received at least one dose of the investigational product. FAS population will be analyzed according to intention-to-treat (ITT) principle, i.e. by treatment allocation regardless happening of intercurrent events (treatment policy strategy). The FAS population will be used for the primary analysis of the study and to present results on efficacy data.

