10.2.2.1 Schirmer I test >10mm/5min at week 8

The proportion of patients reaching a value of Schirmer I test (without anesthesia) >10mm/5min at week 8 will be analyzed as described in section 10.1.2.1 for the primary efficacy endpoints.

10.2.2.2 Change from baseline in SANDE score for severity at week 12

The change from baseline in SANDE score for severity at week 12 will be analyzed as described in section 10.1.2.2 for the primary efficacy endpoints.

10.2.2.3 Change from baseline in SANDE scores for frequency at week 12

The change from baseline in SANDE score for frequency at week 12 will be analyzed as described in section 10.1.2.2 for the primary efficacy endpoints.

10.2.2.4 Change from baseline in IDEEL modules (Quality of Life, Dry eye Treatment satisfaction & Bother, and Dry eye Symptom bother) at week 12 and at week 4

Rules for derivation of IDEEL scores are reported in section 12.3. The change from baseline of each IDEEL module will be analyzed by means of an MMRM adjusting by pre-defined factors (gender, age class, IDEEL module baseline value, treatment, visit, and treatment by visit interaction; subject will be considered as a random effect). The covariance matrix used will be "unstructured". Comparisons versus vehicle TID will be provided using least square means at each visit and overall and a one-sided test will be used to test for differences between treatment groups.

For the imputation of missing data, a regression model will be created by including the baseline value, gender, age class, and intermediate scores up to week 12. Two hundred data sets will be

generated, and the random seed number will be 225670. MI will be implemented in the following steps:

1. Partial imputation assuming MAR will be carried out to impute intermittent (non-monotone) missing data of IDEEL module score based on a multivariate joint Gaussian imputation model using the MCMC method. A separate imputation model will be used for each treatment arm. In case of non-convergence or non-estimability issues, a single imputation model will be considered (with treatment arm added as explanatory variable to the model). A total of 200 datasets will be created. These datasets will be utilized in Step #2.
2. The remaining monotone missing data will be imputed using a MI regression including the same explanatory variables of the previous step. According to MI-RD approach, only non-missing values from retrieve dropouts will be used to inform the regression model.

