3. Each of the 200 imputed datasets will be analyzed using observed and imputed data. Rubin's rule will be used for combining results to draw inference.

If there are not enough retrieved dropouts for convergence of MI-RD regression model, a Copy Reference approach will be adopted to consider a MNAR mechanism for missing data. The final decision on the use of the MI-RD vs Copy-Reference for this endpoint will be done at the time of the analysis and reported in the CSR.

Whether for MI-RD or Copy-Reference approach, the adjusted estimated treatment differences in means for IDEEL module scores between cenegeimin and vehicle at each available timepoint will be displayed together with the corresponding two-side 95% confidence intervals and p-value.

10.2.2.5 Change from baseline in Cornea and conjunctiva vital staining with fluorescein NEI scale at week 4, week 8 and at week 12

Rules for derivation of NEI scores are reported in section 12.4. The change from baseline in Cornea and conjunctiva vital staining with fluorescein NEI scale will be analyzed by means of an MMRM adjusting by pre-defined factors (gender, age class, NEI scale baseline value, treatment, visit, and treatment by visit interaction; subject will be considered as a random effect). The covariance matrix used will be "unstructured". Comparisons versus vehicle TID will be provided using least square means at each visit and overall and a one-sided test will be used to test for differences between treatment groups.

For the imputation of missing data, a regression model will be created by including the baseline value, gender, age class, and intermediate scores up to week 12. Two hundred data sets will be generated, and the random seed number will be 240550. MI will be implemented in the following steps:

1. Partial imputation assuming MAR will be carried out to impute intermittent (non-monotone) missing data of NEI scale score based on a multivariate joint Gaussian imputation model using the MCMC method. A separate imputation model will be used for each treatment arm. In case of non-convergence or non-estimability issues, a single imputation model will be considered (with treatment arm added as explanatory variable to the model). A total of 200 datasets will be created. These datasets will be utilized in Step #2.

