Table 14.2.4.1	Schirmer I test (without anesthesia) >10mm/5min at week 8 - Logistic regression model - Multiple imputation	FAS		X
Table 14.2.4.2	Change from baseline in SANDE scores for severity at week 12. - Analysis of Covariance (ANCOVA) - Multiple imputation	FAS		X
Table 14.2.4.3	Change from baseline in SANDE scores for frequency at week 12. - Analysis of Covariance (ANCOVA) - Multiple imputation	FAS		X
Table 14.2.4.4.1.1	Change from baseline in IDEEL Quality of Life module (Daily activities) up to week 12 - MMRM - Multiple imputation	FAS		X
Table 14.2.4.4.1.2	Change from baseline in IDEEL Quality of Life module (Feelings) up to week 12 - MMRM - Multiple imputation	FAS		X
Table 14.2.4.4.1.3	Change from baseline in IDEEL Quality of Life module (Work) up to week 12 - MMRM - Multiple imputation	FAS		X
Table 14.2.4.4.2.1	Change from baseline in Dry eye Treatment satisfaction & Bother module (Treatment – In General) up to week 12 - MMRM - Multiple imputation	FAS		X
Table 14.2.4.4.2.1	Change from baseline in Dry eye Treatment satisfaction & Bother module (Treatment – Eye drops) up to week 12 - MMRM - Multiple imputation	FAS		X
Table 14.2.4.4.3	Change from baseline in IDEEL Dry eye Symptom bother module up to week 12 - MMRM - Multiple imputation	FAS		X
Table 14.2.4.5	Change from baseline in Cornea and conjunctiva vital staining with fluorescein NEI scale up to week 12 - MMRM - Multiple imputation	FAS		X
Table 14.2.4.6	Change from baseline in TFBUT up to week 12 - MMRM - Multiple imputation	FAS		X
Table 14.2.5.1	Absolute values and change from baseline in Schirmer I test at each timepoint.	FAS	X	X
Table 14.2.5.2.1	Absolute values and change from baseline in SANDE global scores at each timepoint.	FAS	X	X
Table 14.2.5.2.2	Absolute values and change from baseline in SANDE severity scores at each timepoint.	FAS	X	X
Table 14.2.5.2.3	Absolute values and change from baseline in SANDE frequency scores at each timepoint.	FAS	X	X
Table 14.2.5.3	Number of patients experienced a worsening in symptom scores (SANDE global score) and/or NEI score $\geq 50\%$ assessed at week 4	FAS		X

Number	Title	Population	KFR	Final Analysis
Table 14.2.5.4.1	Absolute values and change from baseline in IDEEL Quality of Life module at each timepoint.	FAS	X	X
Table 14.2.5.4.2	Absolute values and change from baseline in IDEEL Dry eye Treatment satisfaction & Bother module at each timepoint.	FAS	X	X

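### The IDEEL Work score is missing by rule for patients who do not work, but the SAP's imputation of missing IDEEL scores makes no exception for scores that do not apply

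*SAP*

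**What the plan says.** - **How the score arises.** In SAP 12.3, Table 4, a patient who answers no to item 22 has no Work score: "then items 23-27 are missing, and the Impact on Work score is missing". The table adds: "The Impact on work score is calculated only when patients answer" yes to that item.
- **How missing IDEEL scores are handled.** SAP 10.2.2.4 fills intermittent gaps by MCMC under MAR, then: "The remaining monotone missing data will be imputed using a MI regression including the same explanatory variables of the previous step". The regression step learns only from retrieved dropouts, or from vehicle patients if Copy Reference is needed. On the model: "a regression model will be created by including the baseline value, gender, age class, and intermediate scores up to week 12". On the analysis: "Each of the 200 imputed datasets will be analyzed using observed and imputed data". SAP 7.9 lists IDEEL among the endpoints to which MI-RD applies.
- **What output is planned.** SAP 15.1, Table 14.2.4.4.1.3, has the title "Change from baseline in IDEEL Quality of Life module (Work) up to week 12 - MMRM - Multiple imputation" and the population FAS. SAP 7.2.4 defines that set without regard to work: "The FAS population will consist of all randomized patients who received at least one dose of the investigational product".
- **What points the other way.** SAP 7.8 says the rules for missing IDEEL data are those of section 12.3 and the manual, although the same section sends the key secondary analyses to MI-RD in 10.2.2. Protocol 9.4.3.3 also refers to the questionnaire manuals.

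**The concern.** A Work score that is absent because the patient has no job is not an unobserved value. There is no work for dry eye to affect, so no true score exists to be recovered. Imputation under any assumption supplies a quantity that has no meaning for that patient.

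The donors are also a poor match. A non-worker who took every dose and attended every visit would receive values modelled on patients who stopped study treatment or, under the fallback, on vehicle patients. The treatment-policy estimand in SAP 7.3 concerns intercurrent events, and having no job at entry is not one. At stake is the treatment difference in the Work table, which would average over workers and over model-generated values for people outside the population the score describes.

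**Working it through.** The documents give no assumption or power for any IDEEL score, so there is no stated figure to reproduce. The check is a reading of the passages in sequence, followed by an illustration of size.

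**Reading**

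1. Not working leads to a missing Work score (SAP 12.3).
2. Missing IDEEL scores are imputed in two steps, and neither step separates a score that does not apply from one that was not obtained (SAP 10.2.2.4).
3. The imputation covariates are the baseline score, gender, age class and intermediate scores. Work status (item 22) is not among them.
4. The Work table is an MMRM after multiple imputation, drawn from a FAS that is not restricted by work status.
5. The pointer to section 12.3 in SAP 7.8 does not break this chain. Section 12.3 ends with a missing score, which is the input to 10.2.2.4.

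**Number of patients**

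Planned enrolment is 90 / (1 − 0.10) = 100. The share not working is an assumption. At 30%, 50% and 70%, the patients with no Work score by rule number 100 × 0.30 = 30, 100 × 0.50 = 50 and 100 × 0.70 = 70 at each visit.

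**Copy Reference**

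Let w be the share working in each arm and δ the true difference among workers. Non-workers in both arms are drawn from the vehicle distribution, so their expected difference is 0 and the expected overall difference is w × δ + (1 − w) × 0 = w × δ. With an assumed δ of 10 points, this is 3, 5 and 7 points for w = 0.3, 0.5 and 0.7.

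A simplified simulation agrees. It used 50 patients per arm, one visit, no covariates, SD 20, 30 imputations pooled by Rubin's rules, one-sided 0.025 and 1,500 runs. δ and the SD are assumptions, not figures from the plan.

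| Share working | Non-workers of 100 | Workers only: estimate, power | Non-workers filled by Copy Reference: estimate, power |
|---|---|---|---|
| 30% | 70 | 9.9 points, 26% | 3.0 points, 0.2% |
| 50% | 50 | 10.0 points, 39% | 5.0 points, 5% |
| 70% | 30 | 9.9 points, 54% | 6.9 points, 26% |

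**MI-RD**

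The result depends on how retrieved dropouts who work happen to score, so the direction cannot be derived. The donor pool is also thin. With an assumed 10 retrieved dropouts, the number expected to have a Work score is 10 × w, which is 3, 5 or 7.

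**The case against.** The strongest reply is that SAP 7.8 makes section 12.3 the specific rule for IDEEL, so that a non-worker's score simply stays missing. Protocol 9.4.3.3 supports that reading. What stands is that the passages conflict and an analyst could follow either. It does not remove the problem, because 7.8 also routes key secondary analyses to MI-RD, 7.9 names IDEEL, and 12.3 gives no instruction beyond setting the score to missing. The departure from the protocol is declared in 7.9; the tension inside the SAP is not.

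Three further points stand in part:

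- The FAS label alone proves little. Tables 14.2.3.1 and 14.2.3.2 are complete-case analyses and carry the same label. It is the label together with the multiple-imputation title and the text of 10.2.2.4 that leads to imputed scores.
- Section 10.2.2.4 speaks of module scores and does not name the Work dimension. Work enters through the appendix table.
- The missing-data rationale in 7.8 concerns patients who discontinue treatment. No text addresses missingness by rule in either direction, so imputation for non-workers follows from the wording and is not stated in words.

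Two stronger readings are tempting and are not supported:

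- A reader might infer that a non-worker's baseline Work score would be imputed too. The SAP uses baseline as a covariate and gives SAS code only for the co-primary endpoints, so the treatment of an absent IDEEL baseline is not stated.
- A reader might infer that the Work result decides test 4.1, and through it the 11 tests after it, or test 4.4. Those tests are on the Quality of Life module, for which 12.3 defines no total, and the appendix has three separate dimension tables. Whether and how Work enters them is undefined.

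**Conclusion.** The concern holds as an unreconciled conflict whose literal reading gives a wrong result: Work scores generated for patients to whom the score does not apply, from a model with no term for work status. It should be corrected, but it affects one dimension of a key secondary endpoint and leaves the co-primary endpoints untouched.

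The size cannot be fixed from the documents. The range of 30 to 70 patients rests on an assumed 30% to 70% not working. Dilution in proportion to the share working is what would be expected under Copy Reference, and the point estimates and powers above rest on an assumed 10-point effect and SD of 20. Nothing here shows an increased risk of a false positive claim.

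**What to change.** Amend the SAP before unblinding:

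- Restrict the Work analysis to FAS patients working at baseline. Baseline status precedes treatment, so the comparison within this subset remains randomised.
- Impute only scores that are unobserved while the patient is working, and never a score that is not applicable.
- State how a patient who starts or stops work is handled, and what is assumed when work status is unknown because the visit was missed. The baseline restriction alone does not settle this.
- Label the population of Table 14.2.4.4.1.3 accordingly.
- Reconcile 7.8 with 10.2.2.4, so that one rule governs missing IDEEL scores.
- Apply the same not-applicable rule to the two Treatment Satisfaction scores that Table 4 sets to missing for patients who use no treatment or no eye drops. This is likely to matter mainly at baseline, since all patients are assigned drops three times daily up to week 12.

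The cost is wording and a smaller sample for this dimension. In the Copy Reference illustration the smaller sample still had more power than the plan as written (26%, 39% and 54% against 0.2%, 5% and 26%).

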12.4 Corneal and Conjunctiva Vital Staining with Fluorescein (NEI scale)

Corneal staining total score is defined as the sum of scores from 5 corneal areas: Central, Superior, Temporal, Nasal, and Inferior. The score for each area ranges from 0 to 3. Thus, the corneal staining total score can range from 0 to 15.

The conjunctiva is divided into a superior paralimbal area, an inferior paralimbal area and a peripheral area with a grading scale of 0–3 and with a maximal score of 9 for the nasal and temporal conjunctiva. Thus, the conjunctival staining total score can range from 0 to 18.

Corneal and conjunctiva vital staining total score is the sum of corneal staining total score and conjunctiva total score.

Information from blinded reading center and site investigators will be used as described in section 7.8.

12.5 Partial date conventions

Table 6: Algorithm for Treatment Emergence of Adverse Events

AE START DATE	AE STOP DATE	RULE for TEAE definition	RULE for “Treatment”/“Follow-up” study period definition for TEAE summaries
Known	Known, Partial or Missing	If AE start date < IMP start date, then not TEAE If AE start date \geq IMP start date, then TEAE	In case of Treatment Discontinuation: If start date \geq Date of last IMP intake, then Follow-up study period for TEAE occurrence. Otherwise, Treatment study period for TEAE occurrence. In case of NO Treatment Discontinuation: If start date \geq Date of “Day 21” visit, then Follow-up study period for TEAE occurrence. Otherwise, Treatment study period for TEAE occurrence.
Partial, but known components show that it cannot be on or after IMP start date	Known, Partial or Missing	Not TEAE	Not applicable

AE START DATE	AE STOP DATE	RULE for TEAE definition	RULE for "Treatment"/"Follow-up" study period definition for TEAE summaries
Partial, could be on or after IMP start date	Known	If AE stop date < IMP start date, then not TEAE If AE stop date \geq IMP start date, then TEAE	If TEAE, then Treatment study period for TEAE occurrence.
	Partial	Impute stop date as latest possible date (i.e. last day of month if day unknown or 31st December if day and month are unknown), then: If AE stop date < IMP start date, then not TEAE If AE stop date \geq IMP start date, then TEAE	
	Missing	Assumed TEAE	
Missing	Known	If AE stop date < IMP start date, then not TEAE If AE stop date \geq IMP start date, then TEAE	If TEAE, then Treatment study period for TEAE occurrence.
	Partial	Impute AE stop date as latest possible date (i.e. last day of month if day unknown or 31st December if day and month are unknown), then: If AE stop date < IMP start date, then not TEAE If AE stop date \geq IMP start date, then TEAE	
	Missing	Assumed TEAE	

NOTE: Assignment to "Treatment" or "Follow-up" study period is applicable only for TEAEs.

Table 7: Algorithm for Prior/Concomitant medications

MEDICATION START DATE	MEDICATION STOP DATE	RULE for prior or concomitant categorization
Known	Known	
If medication stop date < date of first dose of IMP, assign as prior
 
If medication stop date \geq date of first dose of IMP, assign as concomitant

	Partial	
Impute medication stop date as latest possible date (i.e. last day of month if day unknown or 31st December if day and month are unknown), then:
 
If medication stop date < date of first dose of IMP, assign as prior
 
If medication stop date \geq date of first dose of IMP, assign as concomitant

	Missing	Assign as concomitant
Partial or Missing	Known	
If medication stop date < date of first dose of IMP, assign as prior
 
If medication stop date \geq date of first dose of IMP, assign as concomitant

	Partial	
Impute medication stop date as latest possible date (i.e. last day of month if day unknown or 31st December if day and month are unknown), then:
 
If medication stop date < date of first dose of IMP, assign as prior
 
If medication stop date \geq date of first dose of IMP, assign as concomitant

	Missing	Assign as concomitant

13. Tables, Figures and Listings

